Endovascular revascularization of patients with PVD has evolved dramatically. New technology has arisen due to a better understanding of the atherosclerotic process. Treatment modalities encompass balloon angioplasty, stenting, and atherectomy. New modalities of therapy on the horizon include bio-absorbable stents and drug eluting balloons. However, data regarding the effectiveness of these modalities in infra-popliteal disease is scarce. A need exists for reporting on real world data, to document short and long term outcomes.

Metro Health has developed a peripheral vascular intervention program with the on-going goal of being viewed as a center of excellence in the prevention of CLI. In a quest to capture procedure-related details and outcomes related to these approaches, the team at Metro Health has developed an outcomes data registry to measure and report on minimally invasive endovascular therapies, to treat advanced PVD and CLI. Multiple institutions will collectively contribute data to the registry to advance the understanding of patient management and outcomes across all endovascular treatment modalities for advanced PVD and CLI.

2. Objectives:

The primary objective of PRIME is to systematically document endovascular revascularization approaches and patient outcomes with advanced PVD and CLI both inhospital and at 1 month, 3 months, 6 months, and annually for 3 years following treatment. Secondarily, by collecting and summarizing data describing the management and outcomes of these patients, manuscripts will be generated with the goal of improving outcomes. Possible examples include:

- A decrease in the major amputation rate
- A decrease in complications associated with peripheral vascular interventions
- Improvements in the quality of life for patients with advanced PVD and CLI
- Development of mathematical tools to assess risk and outcomes
- Development of standardized testing methodologies
- Development of endovascular treatment guidelines
- Development of follow-up protocols for interventional patients with advanced PVD and CLI
- The promotion of evidence-based care models
- A reduction in the cost of treating patients with advanced PVD and CLI

3. Methods

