Eligible patients with advanced PVD and CLI at medical centers participating in the PRIME Registry will be considered for enrollment in the PRIME registry. Patients will be asked to give consent within 30 days prior and 60 days post index procedure to participate. Once patients are are enrolled, their demographics, medical history, disease-relevant conditions, treatment details and outcomes will be collected for 3 years. Please refer to the initial and follow-up data form for variables collected in the PRIME registry database. Data collected meet the requirements of a "Limited Data Set" as defined by the United States HIPAA regulations. Data contain selected dates but do not include patient names, initials, or medical record numbers. Using web-based data entry this information will be placed into a secure password protected on-line database. Patients are identified in the database by a unique subject record number assigned sequentially by the electronic database and unrelated to their medical record number. This number will follow the patient for the duration of the study. These unique numbers can only be matched with patient identifiers by the individual site coordinator at each institution. It is up to the individual sites to keep a secure key linking the patient and the subject id number for accurate patient follow-up.

Oversight of the PRIME Registry is provided by a Steering Committee and Publications Committee. These committees are comprised of physicians from participating sites and the PRIME Coordinating Center. Decisions regarding protocol changes, investigator roles, addition or deletion of participating sites and publication of abstracts and manuscripts are made by these committees. Data used in abstracts and manuscripts is aggregate data only. No identifiable data is used.

Participant data will be stored in PRIME for an indefinite period of time. Participants will not be informed of the results of retrospective research studies involving the use of their information contained in PRIME.

4. Human Subjects:

Individuals to be approached for participation in PRIME will meet each of the following inclusion criteria:

- a) Adult male and female patients \geq 18 years of age.
- b) Patients who are to receive or have received lower extremity endovascular intervention
- c) Rutherford III-VI Classification
- d) Ability to provide informed consent within 30 day prior to 60 days post endovascular intervention.

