- e) Ability to follow up at enrollment site.

Exclusion Criteria:

Inability or unwillingness to consent for participation in the registry.

Note: Since participation in PRIME does not involve a risk of physical harm, women of childbearing potential will not be queried as to pregnancy status or tested for pregnancy.

5. Recruitment Procedures:

Patients who meet eligibility criteria at participating PRIME centers will be invited to participate in PRIME. Unless otherwise approved, all consecutive patients will be enrolled each month. Due to the voluntary nature of this registry, sites may have limited resources. If all consecutive patients are not able to be enrolled, an alternate method of enrolling patients may be utilized, if used consistently and approved by the site's IRB and the PRIME Steering Committee. Some examples would be enrolling the first 5 or 10 eligible patients each month or enrolling only on odd numbered days. Although the recruitment process may vary by site, potential participants will be approached by a member of the research staff and will be asked to review a copy of the IRB-approved informed consent form. The research staff will review the consent form and address any questions or concerns prior to obtaining written informed consent for PRIME participation. The research staff will also address any future questions or concerns that may occur. To insure lack of selection bias, a screening log of subjects who meet eligibility criteria, but decline consent, will be kept at the site. A de-identified version of this list will be provided to the coordinating center on request.

6. Potential Risks of Research Registry Participation:

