Once the decision is made by the PRIME Steering Committee to add a new site, the Coordinating Center will communicate with that site to insure all regulatory documents are completed. PRIME Registry members are required to have active IRB approval and a signed data use agreement to participate in PRIME. Only after these documents are received by the Coordinating Center are users at each site issued log-ons and passwords for the database. Patient consent requirements are determined by each site's IRB. IRB approval must be updated regularly based on the schedule determined by each institution's review board. Sites that have not maintained IRB approval may not continue to add patients to the registry until their IRB approval is obtained.

In order to ensure data accuracy, periodic auditing of participating sites will be conducted. The PRIME Coordinating Center will receive de-identified source documents for the first five patients enrolled at each new center; additionally, documentation for subsequent patients may be requested if deemed necessary by the reviewers. Further adjudication may be performed at random intervals.

10. Statistical Design:

Coordinating Center statisticians combine data collected from all sites in aggregate tables. Only aggregate data is used in analysis. No identifiable data are used.

Continuous data shall be expressed as means +/-standard deviations or medians (Q1-Q3) as appropriate. Discrete data shall be expressed as counts and percentages. Chi-squared, Fisher's exact tests and student's t-tests may be used as appropriate to determine statistical significance. Linear and logistic regression and survival analysis may be applied to create statistical models.

11. Protocol References:

- 1. Shammas NW. Epidemiology, classification, and modifiable risk factors of peripheral arterial disease. Vasc Health Risk Manag 2007;3(2):229-34.

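### Section 10 requires only counts and percentages for event outcomes followed to 3 years; with incomplete follow-up these crude rates are biased, and consent after the procedure separately lowers early mortality.

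*Combined protocol and SAP*

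**What the plan says.** Section 10 (Statistical Design) is the whole statistical plan. Its mandatory summaries are means or medians for continuous data and, for everything else, "Discrete data shall be expressed as counts and percentages". Tests and models are optional: "Linear and logistic regression and survival analysis may be applied to create statistical models". The section gives no denominator for the percentages, no rule for patients lost to follow-up, and no rule for death before amputation.

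Section 2 (Objectives) makes it the primary objective to document outcomes in hospital, at months 1, 3 and 6, and "annually for 3 years following treatment". The first listed example of what the manuscripts might achieve is "A decrease in the major amputation rate".

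On entry, Section 3 (Methods) says "Patients will be asked to give consent within 30 days prior and 60 days post index procedure to participate", and Section 4 (Human Subjects) has the matching criterion "Ability to provide informed consent within 30 day prior to 60 days post endovascular intervention". Section 4 also admits patients who have already been treated. The only provision that bears on loss is another entry criterion, "Ability to follow up at enrollment site". On the data held, Section 3 says "Data contain selected dates"; the data forms are not part of the text.

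**The concern.** Amputation, reintervention and death over 3 years are time-dependent events in a population where some patients will die and some may stop attending. A crude percentage takes no account of how long each patient was observed. If follow-up is incomplete, the result depends on retention and on a denominator that the plan does not state. Groups or sites with the same true risk but different retention can then appear to differ. Kaplan-Meier with deaths censored, a familiar alternative, brings a different error: it overstates the risk of amputation.

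The consent window raises a second, smaller issue. A patient who would have consented after the procedure but died first never enters the registry. If late consenters are counted from the procedure, their survival up to consent is guaranteed, and early mortality comes out too low.

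**Working it through.** The plan states no event rate, loss rate or sample size, so there is no figure of its own to reproduce. All rates below are assumptions, chosen to show direction and range.

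**Loss to follow-up.** Take constant yearly hazards a (amputation), d (death) and c (loss), with loss independent of outcome, T = 3 years and s = a + d + c.

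- True risk = a/(a+d) × (1 − exp(−(a+d)T))
- Crude, all enrolled = a/s × (1 − exp(−sT))
- Lost first = c/s × (1 − exp(−sT))
- Crude, known status = (crude, all enrolled)/(1 − lost first)
- 1 − Kaplan-Meier, deaths censored = 1 − exp(−aT)

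For a = 0.08, d = 0.20, c = 0.15:

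- True: 0.08/0.28 × (1 − exp(−0.84)) = 16.24%
- All enrolled: 0.08/0.43 × (1 − exp(−1.29)) = 13.48%
- Lost first: 0.15/0.43 × (1 − exp(−1.29)) = 25.28%
- Known status: 13.48/(1 − 0.2528) = 18.05% (18.0% where one decimal is given, from unrounded values)
- 1 − Kaplan-Meier: 1 − exp(−0.24) = 21.34%

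3-year amputation risk over a range of assumptions:

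| a, d, c | True | All enrolled | Known status |
|---|---|---|---|
| 0.08, 0.20, 0 | 16.24% | 16.24% | 16.24% |
| 0.08, 0.20, 0.05 | 16.24% | 15.23% | 16.84% |
| 0.08, 0.20, 0.15 | 16.24% | 13.48% | 18.05% |
| 0.08, 0.20, 0.25 | 16.24% | 12.02% | 19.24% |
| 0.05, 0.10, 0.02 | 12.08% | 11.75% | 12.33% |
| 0.05, 0.10, 0.05 | 12.08% | 11.28% | 12.71% |

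The first row shows that with no loss the crude percentage is correct, even with substantial mortality. At 1 year with hazards 0.08, 0.20 and 0.15 the gap is still small: 6.98% true, 6.50% and 7.40%. For 3-year mortality (d = 0.20, c = 0.15, using the same formulas for death and loss alone), the truth is 45.12%, against 37.15% over all enrolled and 51.49% over known status.

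Rows two and four can be read as two groups with equal true risk and unequal retention. Over all enrolled, the better-retained group looks worse (15.2% against 12.0%). Over known status it looks better (16.8% against 19.2%). The apparent order depends on the denominator.

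**Loss that depends on risk.** Take two equal strata with amputation hazards 0.02 and 0.14, loss hazards 0.03 and 0.40, and death hazard 0.20 in both. The true 3-year risk is 15.4%. Known status gives 14.5%, now too low, and unadjusted Aalen-Johansen gives 12.8%, which is further off. With amputation 0.04/0.12 and loss 0.05/0.25, the truth is 15.8%, known status 16.4% and Aalen-Johansen 14.9%.

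**Consent after the procedure.** Let a share p consent after the procedure, at a day U spread evenly over days 0 to 60, with d = 0.20 a year. Mortality at T, counted naively from the procedure, is [(1−p)(1−exp(−dT)) + p·E{exp(−dU) − exp(−dT) if U < T, else 0}] / [(1−p) + p·E{exp(−dU)}]. Consent spread evenly over days −30 to 60 gives p = 60/90 = 2/3.

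| Time | True | Naive, p = 2/3 |
|---|---|---|
| 5 days | 0.27% | 0.10% |
| 30 days | 1.63% | 0.82% |
| 90 days | 4.81% | 3.77% |
| 1 year | 18.13% | 17.23% |
| 3 years | 45.12% | 44.52% |

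With p = 1/3 the 30-day figure is 1.23%.

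**Check of the remedy.** In 400,000 simulated patients (hazards 0.08, 0.20 and 0.15; consent even over days −30 to 60; loss and consent timing independent of outcome), Aalen-Johansen with entry at consent gave 3-year amputation of 16.26%. Kaplan-Meier with entry at consent gave mortality of 1.64% at 30 days and 45.08% at 3 years.

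**The case against.** This is a descriptive registry with no confirmatory hypothesis. The sentence on percentages is a general reporting convention, and survival analysis is available to Coordinating Center statisticians, who analyse centrally under committee oversight. That stands in part. A reader might infer that the plan excludes survival methods, or that its manuscripts will contradict one another; the text supports neither. What remains is that describing outcomes is itself the objective, and the one binding rule for describing events ignores follow-up time.

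A reader might also infer that follow-up has no time origin. Section 2 counts from treatment and Section 3 refers to the index procedure, so the origin is implied.

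The strongest technical objection is that the upward direction for known-status percentages needs loss to be independent of outcome. This stands: the risk-dependent example reverses it, and there the standard competing-risks estimator does worse than the crude figure. The remedy therefore needs a sensitivity analysis.

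The magnitudes are assumed, and ability to attend follow-up is an entry criterion, so actual loss may be low. That also stands. On late entry, Section 9 leaves consent requirements to each site's IRB, so the effect arises only where consent is in fact obtained after the procedure. Sections 3 to 5 expect consent, and Section 5 expects it in writing.

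**Conclusion.** The point holds in a conditional form and should be fixed; confidence is medium. With incomplete follow-up, the percentage over all enrolled is too low because events after loss are missed. Over known status it is too high if loss is independent of outcome; otherwise the direction can change. For 3-year amputation the gap is about 0.3 to 0.8 points at the mild assumed rates, and 2 to 3 points at yearly hazards of 0.08, 0.20 and 0.15, where 25% are lost first. Kaplan-Meier with deaths censored gives 21.3% against 16.2% in that case.

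The late-consent effect is separate and early. It lowers in-hospital, 1-month and 3-month mortality, and a reader should not carry it over to 3-year rates, where the difference is 0.6 points on 45.1%. Nor do the documents support saying that the registry's rates will be wrong by any particular amount: with complete follow-up the crude percentage is unbiased. A lower amputation risk because more patients die first is a real absolute risk, not a bias.

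**What to change.** In Section 10, keep counts and percentages, with the denominator stated, for baseline and procedural items. For post-discharge events:

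- Report cumulative incidence with 95% confidence intervals at the scheduled visits, counted from the index procedure.
- Treat death as a competing event for amputation and reintervention (Aalen-Johansen). Use Kaplan-Meier for overall and amputation-free survival.
- Censor at last contact. Report numbers at risk and completeness of follow-up by group and site.
- Let patients who consent after the procedure enter the risk set at consent, and list their earlier events separately.

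Report in-hospital and 1-month mortality with this delayed entry, or only in patients who consented before the procedure, and not as a crude percentage of all enrolled. State that the methods assume uninformative loss and consent timing, and add a sensitivity analysis, for example weighting for loss by baseline covariates.

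The cost is about a paragraph of text and standard routines. Tables become slightly more complex, and few patients will be at risk in the first weeks if most consent late. The coordinating center must confirm that the dates held include procedure, consent, event and last contact.

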There are no risks of physical harm associated with participation in PRIME as this is an observational registry only and no treatment is added or dropped due to a patient's participation in the registry. Participation in PRIME does involve the potential risks of a breach of confidentiality of the medical record information and associated privacy of the participants. Such risks will be minimized by 1) removing direct participant identifiers (i.e., there will be no names, social security numbers, medical record numbers recorded); 2) placing recorded information on a secure server with limited access to information linking unique subject record numbers with direct participant identifiers; and 3) limiting access to the PRIME database to the appropriate IRB-approved staff at each site. Each user at a site will have his or her own log-on and password to access the database. Obtaining access to the database allows research staff the ability to enter patients' clinical data and to view their site's data. Site users are unable to access or view data from other sites.

7. Potential Benefits of Research Registry Participation:

There are no direct benefits associated with participation in PRIME. However, the use of information contained within PRIME for retrospective analyses may be of future benefit to patients with PVD. Participants in PRIME will be informed of future research studies involving PVD for which they may be eligible if they so desire.

8. Costs and Payments:

All costs associated with the implementation and maintenance of PRIME shall be supported by Metro Health through institutional support and unrestricted grants from industry. No costs will be incurred by PRIME participants. Patients will not be remunerated for their participation in PRIME. Similarly, as this is a voluntary registry, sites will not be paid to participate in the registry.

9. Addition of PRIME Registry Sites:

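### Does Section 10 make treatment-modality comparisons rest on unadjusted tests pooled across sites?

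*Combined protocol and SAP*

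**What the plan says.** Section 10 (Statistical Design) is the whole statistical plan. On pooling it says "Coordinating Center statisticians combine data collected from all sites in aggregate tables". On testing it says "Chi-squared, Fisher's exact tests and student's t-tests may be used as appropriate to determine statistical significance". On modelling it says "Linear and logistic regression and survival analysis may be applied to create statistical models". It names no outcome, exposure, covariate, stratum or site term for any of these, and no other section supplies one.

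The setting comes from the other sections:

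- **Objective (Section 2).** The primary objective is to record revascularisation approaches and patient outcomes in hospital and out to 3 years. Manuscripts are a secondary aim, with nine possible examples of what they might lead to. One is "Development of endovascular treatment guidelines"; another is building mathematical tools for risk and outcome.
- **Background (Section 1).** On the treatment modalities, it says that "data regarding the effectiveness of these modalities in infra-popliteal disease is scarce".
- **Allocation (Section 6).** The protocol states that "this is an observational registry only and no treatment is added or dropped" because a patient takes part.
- **Population (Section 4).** Eligibility covers "Rutherford III-VI Classification".
- **Data (Section 3).** For enrolled patients, "their demographics, medical history, disease-relevant conditions, treatment details and outcomes will be collected for 3 years".

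**The concern.** The only sentence in the plan that mentions statistical significance lists three procedures, none of which takes a covariate. The models come in a separate sentence, as something that may be applied, with no instruction to use them for comparisons. Taken together with the pooling of sites, this can be read as a plan to judge modality differences by crude tests on the combined data.

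That would matter because the registry does not assign treatment and its patients span a wide range of severity. Section 1 says that amputation trends vary by location, and Section 5 lets sites use different approved enrolment schemes, so outcomes and case mix may well differ between sites. If sicker patients, or particular sites, tend to receive one modality, a crude difference mixes that selection with any treatment effect. A manuscript feeding into treatment guidelines could then report as a modality effect something that reflects who was treated, or where.

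**Working it through.** **No figure to reproduce.** The documents give no sample size, significance level, event rate, modality split, severity mix, number of sites or within-site correlation (ICC). Every input below is an assumption, chosen to show how the mechanism behaves. There is no true modality effect unless stated, and tests are two-sided at 5%.

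**Step 1: severity only.** Let a share s of each group be severe, with event risk rH if severe and rL otherwise. The crude risk is p = s·rH + (1 − s)·rL.

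With s = 0.6 and 0.3, rH = 0.12 and rL = 0.06:

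- pA = 0.6 × 0.12 + 0.4 × 0.06 = 0.096
- pB = 0.3 × 0.12 + 0.7 × 0.06 = 0.078
- Crude risk ratio = 0.096 / 0.078 = 1.23

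At n = 500 per group the pooled risk is 0.087.

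- Null standard error: √(2 × 0.087 × 0.913 / 500) = 0.01783
- Standard error at the actual risks: √((0.096 × 0.904 + 0.078 × 0.922) / 500) = 0.01782
- Rejection probability: Φ((0.018 − 1.96 × 0.01783) / 0.01782) + Φ((−0.018 − 1.96 × 0.01783) / 0.01782) = 0.171 + 0.001 = 0.172

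Other cases by the same formula:

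| Severe share | Risk, severe / not | Crude RR | Rejection, 500 per group | Rejection, 200 per group |
|---|---|---|---|---|
| 60% / 30% | 12% / 6% | 1.23 | 17.2% | 9.8% |
| 60% / 30% | 15% / 3% | 1.55 | 53.7% | 25.4% |
| 50% / 40% | 12% / 6% | 1.07 | 6.3% | 5.5% |
| 45% / 45% | any | 1.00 | 5% | 5% |

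In simulation, a severity-stratified test rejects 4.7–5.2% in every cell.

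**Step 2: site only (simulation).** Assume 20 sites of 50 patients, a 10% event rate and ICC 0.02. Half the sites favour one modality and half the other. The crude test rejects 12.2% of the time when the within-site modality split is 90:10, 6.8% at 70:30 and 4.9% at 50:50. Over ICC 0.01–0.05 the ranges are 8.8–21.3%, 5.8–9.1% and 4.7–4.9%. A site-stratified Mantel-Haenszel test stays at 4.8–5.4%.

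**Step 3: both together (simulation).** Same sites, ICC 0.02, risk 12% against 6%. The model is logistic, with severity and site as fixed effects.

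| Modality split by site | Severe share | Crude test | Model |
|---|---|---|---|
| 90:10 | 60% / 30% | 22% | 5.1% |
| 70:30 | 60% / 30% | 18% | 5.2% |
| 70:30 | 50% / 40% | 8.1% | 5.3% |
| 50:50 | 45% / 45% | 4.9% | 5.3% |

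**Step 4: what mandatory site adjustment costs.** If inference rests on within-site contrasts, the standard error grows by √(0.25 / (s(1 − s))), where s is now the within-site modality share.

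- 90:10: √(0.25 / 0.09) = 1.67
- 70:30: √(0.25 / 0.21) = 1.09
- 50:50: 1.00

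With an assumed true odds ratio of 0.5 and no severity imbalance, simulated model power is 36%, 68% and 75% respectively. The crude test shows 71%, 74% and 74%, but its 71% is not valid power, because its type I error at 90:10 is 11.6%.

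**Step 5: how much adjustment repairs.** The 5% rates in Steps 1–3 arise because the simulated confounders are exactly the ones adjusted for. Add one further factor that is left out (prevalence 60% against 30%, risk ratio 2) and the severity-stratified test again rejects 17% at 500 per group and 10% at 200.

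**Step 6: the text against the mechanism.** The inflation needs three things: a modality comparison, imbalance in severity or site, and inference from the crude test alone. The plan states no such comparison, is silent on imbalance, and does not confine inference to the crude tests. The testing sentence is permissive, and the models allowed in the next sentence give their own p-values and intervals. Section 10 also says that only aggregate data enter the analysis. Read literally, that would rule out the patient-level regression the same section allows. Since it is paired with a statement about identifiable data, it is better read as a privacy statement.

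**The case for a change.** The strongest case for a change is that modality comparisons are foreseeable. Section 1 points to scarce effectiveness data and says the sites' pooled data are meant to improve understanding of outcomes across all modalities. Section 2 makes manuscripts an aim, and Section 10 provides significance tests, which pure description would not need. Two or three sentences requiring adjusted models for such comparisons would cost little, since the models are already permitted and the relevant kinds of data are collected. Without randomisation, an unadjusted test cannot by itself separate modality from case mix, whatever the size of the bias.

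Much of this stands. The plan names no severity or site term, and a manuscript that claimed a modality effect from crude tests alone would deserve challenge. It does not follow that the master protocol must fix the model. The guideline item is one of nine possible outputs, and the remark about scarce data leads into a call for real-world reporting. The tests also have ordinary descriptive uses. Risk modelling is itself among the anticipated outputs, and Section 3 gives the Steering and Publications Committees the decisions on abstracts and manuscripts, so covariates can be set for each manuscript. A single rule written now would also have to choose between site fixed effects, random effects and clustered variance before the modality split by site is known; Step 4 shows that this choice can be costly. A minimum set of Rutherford class, age and site would still omit the lesion complexity and comorbidity that Section 1 stresses.

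**Conclusion.** No change is needed. Section 10 permits unadjusted tests and multivariable models alike and leaves the choice to the analyst, which is usual for a registry with open-ended manuscripts. Followed as written, it gives sound descriptive results for the primary objective. The hazard arises only if a later manuscript makes an unplanned modality comparison and rests it on the crude tests.

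In that event the false-positive rate could lie anywhere from 5% with balance to about 54% in the most extreme severity case above. That range depends wholly on assumed severity shares, event risks, group sizes, site structure and ICC, and on a two-group comparison, whereas Section 1 names three established modalities. The documents do not show where in it the registry would fall. Any analyst making such a comparison would be expected to adjust for baseline severity and account for site, and can do so under the present text; residual confounding would remain either way.
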